1.3. Rationale for the clinical study and study design

A Phase IIa study (ABX464-101) aimed at evaluating the efficacy and safety of ABX464 given at a fixed dose of 50mg once daily versus Placebo in Patients with Moderate to Severe Active Ulcerative Colitis who have failed or are Intolerant to immunomodulators, Anti-TNF α or Corticosteroids was conducted in Belgium, France, Germany, Austria, Poland, Hungary.

32 patients were randomized (23 ABX464 patients/9 placebo). The principal study results are presented below.

A strong efficacy signal was observed with ABX464 50 mg:

- Clinical Remission rate of 35.0 % of ABX464 patients (Placebo = 11.1%)
- Endoscopic improvement rate of 50.0 %* (p=0.03) of ABX464 patients (Placebo = 11.1%)
- Clinical Response rate of 70.0 % of ABX464 patients (Placebo = 33.0%)

Same results were also observed in Total and Partial Mayo Score, as depicted in the following graphs

[figure not shown]

Figure 5: Mean change in Total and Partial Mayo in ABX464-101 study

At the end of the completed 2 months induction treatment study, 22 Patients (15 previously treated with ABX464 and 7 on placebo) were enrolled into the open-label maintenance study with ABX464 50mg daily (ABX464-102) regardless of what treatment they had previously received. An interim analysis of this maintenance study was performed after all patients had completed at least 12 months dosing in the maintenance study, with a mean ABX464 treatment duration in the maintenance study of 422 days.

The interim analysis used the Month 12 Per Protocol (M12 PP) dataset which included all subjects that had a Month 12 visit. Of the 22 subjects, 3 subjects were excluded from the M12 PP Set: 2 subjects from the ABX464 induction group (one who withdrew due to lack of efficacy at M1 of the maintenance study and one who was lost to follow-up) and 1 subject from the placebo induction group (grade 2 headache at month 4), resulting in 19 subjects analyzed in the efficacy M12 PP set at baseline. Of the nineteen subjects in the set, sixteen had had a Month 12 endoscopy performed which forms part of the Total Mayo score (TMS).

Clinical remissions obtained at the end of the induction study were durable and the rates further improved during the maintenance phase, as additional subjects achieved clinical remission during 12 months treatment.

All patients who had an endoscopy performed, had an endoscopic subscore of 0 or 1. 12/16 patients were in clinical remission at month 12.

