3.1.1. Design and methodology

This phase IIb study will evaluate the efficacy and the safety of 3 dose-levels of ABX464, administered daily in improving Modified Mayo Score (MMS) in patients with moderate to severe Ulcerative Colitis at Week 8.

Eligible patients will be randomized into 4 parallel intervention/treatment groups:

Intervention/treatment Active Arm	
Group #1: 25mg qd	1 capsule of 25mg ABX464 + 1 capsule of Placebo
Group #2: 50mg qd	1 capsule of 50mg ABX464 + 1 capsule of Placebo
Group #3: 100mg qd	2 capsules of 50mg ABX464
Group #4: Placebo	2 capsules of Placebo

The study design is presented below:

At Week 16, regardless of their clinical/symptomatic response and the actual treatment/dose received, patients willing to continue the study treatment and eligible for enrollment will roll over in an Open Label Extension study (ABX464-104). In this extension study, all patients will be dosed with ABX464 50mg QD. ABX464-104 is a separate clinical protocol subject to health authorities and ethics committee approvals.

In the present induction study (ABX464-103), randomization will be stratified according to the following factors:

- 1) US versus non-US patients
- 2) patients without previous exposure to biological or JAK inhibitors versus patients with previous exposure to biological drugs or JAK inhibitors.

The proportion of patients with previous exposure to biologics or JAK inhibitors will be limited to 60%, including a maximal proportion of patients with previous treatment with vedolizumab of 20%. The maximal proportion of patients with previous exposure with JAK inhibitors will be limited to 10%.

Patients will be treated for 16 Weeks in this induction study. All endoscopies (videos) will be centrally reviewed. E-Diaries will be used to collect frequency of stools, rectal bleedings, number of capsules taken and the intake time.

From Day 1 onwards, randomized patients will be seen at the investigational site on a regular basis (cf. flow-chart).

Flexible sigmoidoscopy with rectal and sigmoidal (if the sigmoidal is inflamed) biopsies will be performed at screening, at Day 57 +/- 4 days (week 8) and at Day 113 +/- 4 days (week 16). The Day 113 measurement will only be taken if patient does not experience endoscopic improvement at Day 57 (i.e.:

endoscopy sub-score of 2 or 3).

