Flexible sigmoidoscopy with rectal and/or sigmoidal biopsies will be performed at screening, at Day 57 +/- 4 days (Week 8) and at Day 113 +/- 4 days (Week 16). The Day 113 measurement will only be taken if the patient does not experience endoscopic improvement (i.e. endoscopy sub-score of 2 or 3) at Day 57. In the event of clinical progression of the disease after Week 8, defined as at least a 2-point increase from screening in pMMS, with a MMS ≥ 4 confirmed by an endoscopy sub score of 2 points or higher, the patient will exit the study.

Study Design

Document: \\ieedc-vnasc01\BIOSdata\Abivax\ABX464\FZA92720\Biostatistics\Documentation\SAP\ABX464-103_SAP_V2.0_10MAY2021

Author: [REDACTED]

Version Number: 2.0
Version Date: 10May2021

Template No.: CS_TP_BS016 Revision 5

Reference: CS_WI_BS005

Effective Date: 01Apr2018

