Percentage of patients with clinical response at Week 8 and Week 16

$$= \frac{\text{Number of patients in treatment arm with clinical remission at Week 8 and Week 16}}{\text{Total number of patients in the treatment arm}} \times 100$$

Number of patients with clinical response at week8 and not at week 16 as well as number of patients with clinical response at Week 16 and not at Week 8 will also be presented.

Document: \\ieedc-vnasc01\BIOSdata\Abivax\ABX464\FZA92720\Biostatistics\Documentation\SAP\ABX464-103_SAP_V2.0_10MAY2021

Author: [REDACTED]

Version Number: 2.0
Version Date: 10May2021

Template No.: CS_TP_BS016 Revision 5

Reference: CS_WI_BS005

Effective Date: 01Apr2018

15.2.1.4. Number and Percentage of Patients with Endoscopic Improvement and Remission, by Segment at Week 8 and Week 16

Endoscopic improvement is defined as an endoscopic sub-score ≤ 1 and endoscopic remission is defined as an endoscopic sub-score = 0. The improvement and remission will be summarized by segment (descending colon, sigmoid colon, rectum) as well as overall endoscopic improvement and remission for Week 8 and Week 16.

Percentage of patients with endoscopic improvement (or remission) at Week 8 for segment X

$$= \frac{\text{Number of patients in treatment arm with endoscopic improvement (or remission) at Week 8 in segment X}}{\text{Total number of patients in the treatment arm for segment X at Week 8}} \times 100$$

The percentage of patients with endoscopic improvement or remission at Week 16 for segment X will be calculated similarly for data available at Week 16.

The overall percentage of patients with endoscopic improvement or remission at Week 8 will be calculated as follows:

Percentage of patients with endoscopic improvement (or remission) at Week 8 =

$$= \frac{\text{Number of patients in treatment arm with endoscopic improvement (or remission) at Week 8}}{\text{Total number of patients in the treatment arm at Week 8}} \times 100$$

The overall percentage of patients with endoscopic improvement or remission at Week 16 will be calculated similarly for data available at Week 16.

Number of patients with endoscopic improvement and endoscopic remission, by segment at week8 and not at week 16 as well as number of patients with endoscopic improvement and endoscopic remission, by segment at Week 16 and not at Week 8 will also be presented.

Document: \\ieddc-vnasc01\BIOSdata\Abivax\ABX464\FZA92720\Biostatistics\Documentation\SAP\ABX464-103_SAP_V2.0_10MAY2021

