15.2.3. ANALYSIS OF SECONDARY EFFICACY VARIABLES

15.2.3.1. Analysis of Secondary Variables at Week 8 and at Week 16

In addition to the descriptive statistics as described in Section 15.2 and specific subsections of Section 15.2. ANCOVA models, using the same procedure as described for the primary efficacy analysis in section 15.1.3, will be used to make the assessments listed below:

- Global effect of ABX464 treatment vs placebo in change from baseline in MMS at Week 8
- Combined number and percentage of patients in clinical remission at Week 8 and Week 16
- The number and percentage of patients with clinical response at Week 8 and Week 16
- The number and percentage of patients with endoscopic improvement and remission, by segment at Week 8 and Week 16
- Proportion of patients with mucosal healing at Week 8 and Week 16
- Daily stool frequency and number of patients with reduction relative to baseline in stool frequency sub-score at every study visit
- Number of patients with reduction relative to baseline in rectal bleeding sub-score at each visit
- Frequencies and percentages for rectal bleeding and stool frequency sub-score categories
- Frequencies and percentages for Mucosal Appearance at endoscopy by segment
- Total IBDQ scores and change from baseline at Week 8 and Week 16

In addition, the above variables will be included in a listing by patient. The frequency of daily stools and categories of rectal bleeding as recorded in the e-Diary will be listed for the duration of the study.

[REDACTED]

[REDACTED]

[REDACTED]

Document: \\ieddc-vnasc01\BIOSdata\Abivax\ABX464\FZA92720\Biostatistics\Documentation\SAP\ABX464-103_SAP_V2.0_10MAY2021

Author: [REDACTED]

Version Number: 2.0
Version Date: 10May2021

Template No.: CS_TP_BS016 Revision 5

Reference: CS_WI_BS005

Effective Date: 01Apr2018

15.2.3.2. Analysis of Number and Percentage of Patients in Clinical Remission at Week 8

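### Week 16 endoscopic improvement is calculated only in patients who had not improved at Week 8, so the planned Week 16 comparison does not estimate the effect of each dose against placebo

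*SAP*

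**What the plan says.** **Who has a Week 16 endoscopy.** Protocol 3.1.1: "The Day 113 measurement will only be taken if patient does not experience endoscopic improvement at Day 57". SAP 3.1 repeats the rule: the measurement "will only be taken if the patient does not experience endoscopic improvement (i.e. endoscopy sub-score of 2 or 3) at Day 57". The biopsies belong to the same procedure.

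**Endpoint definitions.** SAP 15.2.1.4: "Endoscopic improvement is defined as an endoscopic sub-score ≤ 1 and endoscopic remission is defined as an endoscopic sub-score = 0". Mucosal healing (SAP 15.2.1.5) needs endoscopic remission and histological remission together.

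**Denominators.** SAP 15.2.1.4: "The overall percentage of patients with endoscopic improvement or remission at Week 16 will be calculated similarly for data available at Week 16". It applies the same basis to the Week 16 percentages by segment. SAP 15.2.1.5 divides mucosal healing by the patients in the arm at the visit. It does not say whether that means patients who were re-scoped or all who attended.

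**Between-arm comparison.** The ANCOVA list in SAP 15.2.3.1 includes "The number and percentage of patients with endoscopic improvement and remission, by segment at Week 8 and Week 16" and "Proportion of patients with mucosal healing at Week 8 and Week 16". The objective in Protocol 2.2 and SAP 2.2 is the effect of each dose group against placebo on these endpoints, at Week 16 if available.

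**Missing data.** The imputation in SAP 7.3 covers Week 8 only, and SAP 15.2.2 refers back to it. No rule carries a Week 8 improver forward. SAP 15.2.1.1 defines a composite of Week 8 or Week 16 for clinical remission, but there is none for the endoscopic endpoints or mucosal healing.

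**Extra counts.** SAP 15.2.1.4 (by segment) and 15.2.1.5 also plan counts of patients who meet the endpoint at Week 8 but not at Week 16.

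**The concern.** The decision to re-scope is made after randomization and depends on the outcome being measured. A Week 8 improver has no scheduled Week 16 endoscopy, so is absent from the Week 16 denominator for overall improvement. The more a dose achieves by Week 8, the more of its successes leave that denominator and the more the remainder is made up of its harder cases. The groups left in each arm are then not comparable as randomized.

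For remission and mucosal healing the rule removes Week 8 scores of 0 and also of 1. It therefore takes out patients who had already reached the endpoint and patients who had not.

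At stake is whether a reader of the Week 16 tables would see little, no or reversed benefit for a dose whose whole-arm improvement is better than placebo.

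**Working it through.** The documents give no expected rate or power for the Week 16 endoscopic endpoints, so there is no planned figure to reproduce. What follows illustrates overall improvement only.

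**Inputs**
- *p*, improvement rate at Week 8: 50.0% active and 11.1% placebo, from the 32-patient Phase IIa study in Protocol 1.3 (23 active, 9 placebo randomized).
- *m*, share of Week 8 improvers still improved at Week 16: assumed 90%, then varied.
- *c*, share of Week 8 non-improvers who convert by Week 16: assumed, shown as a range.

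**Formulas**
- Rate the SAP would report at Week 16 = *c*.
- Whole-arm rate at Week 16 = *p*·*m* + (1 − *p*)·*c* = *c* + *p*(*m* − *c*).
- Whole-arm difference minus reported difference = *p*ₐ(*m* − *c*ₐ) − *p*ₚ(*m* − *c*ₚ), with subscripts a for active and p for placebo.

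**Denominators.** The re-scoped share is 1 − 0.500 = 50% of active and 1 − 0.111 = 89% of placebo patients. With 61 per arm and 5% dropout (61 × 0.95 = 58), that is about 29 against 52 patients.

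**Results at *m* = 0.9.** First row: active 0.500 × 0.9 + 0.500 × 0.20 = 0.550; placebo 0.111 × 0.9 + 0.889 × 0.20 = 0.278.

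| Conversion, active / placebo | Whole-arm rates | Whole-arm difference | Reported difference | Shortfall as share of whole-arm difference |
|---|---|---|---|---|
| 20% / 20% | 55.0% / 27.8% | 27.2 points | 0 | 100% |
| 10% / 15% | 50.0% / 23.3% | 26.7 points | −5 | 119% |
| 20% / 10% | 55.0% / 18.9% | 36.1 points | 10 | 72% |
| 30% / 10% | 60.0% / 18.9% | 41.1 points | 20 | 51% |
| 40% / 10% | 65.0% / 18.9% | 46.1 points | 30 | 35% |

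**Sensitivity.** With equal conversion in both arms the reported difference is always 0, and the whole-arm difference is (*p*ₐ − *p*ₚ)(*m* − *c*). Take conversion from 10% to 30% and retention from 80% to 100%. At the Phase IIa rates this runs from 0.389 × 0.5 = 0.19 to 0.389 × 0.9 = 0.35. At milder Week 8 rates of 40% against 20% (an assumption) it runs from 0.20 × 0.5 = 0.10 to 0.20 × 0.9 = 0.18.

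**Mucosal healing.** The documents give no rates, so no figure is computed for this endpoint. If the denominator is re-scoped patients, the selection is as above. If it is all Week 16 attenders, a Week 8 improver stays in the denominator but cannot count as healed, having no scheduled endoscopy or biopsy. The direction can be seen from the same arithmetic applied to improvement. With 20% conversion in both arms, (1 − *p*)·*c* is 0.500 × 0.20 = 10.0% active and 0.889 × 0.20 = 17.8% placebo, which runs against the better arm.

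**The case against.** **The plan says 'if available', and the endpoints are secondary.** This is true. They sit outside the gatekeeping in SAP 7.4. Protocol 9.2 plans descriptive statistics for secondary variables, names no Week 16 endoscopic or mucosal test, and treats p-values from its additional analyses as descriptive. This limits the consequence. It does not make the data ignorably missing, because availability is set by the outcome, and a descriptive table on this denominator misleads in the same way.

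**A reader might infer that the trial could choose the wrong dose.** The documents do not support that. The primary objective selects the dose on change in MMS at Week 8, and the ordered tests concern that endpoint alone.

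**A reader might infer that mucosal healing is calculated only on re-scoped patients.** SAP 15.2.1.5 does not carry the available-data wording of 15.2.1.4. Its denominator is ambiguous, though neither reading lets a Week 8 improver count as healed at Week 16.

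**A reader might infer that none of the counts of Week 8 but not Week 16 can be evaluated.** That goes too far for segments. The re-scope rule uses the endoscopy sub-score, and the documents do not say how it relates to segment scores. If it reflects the worst segment (an assumption), a re-scoped patient may have had an improved segment at Week 8 and have Week 16 data for it. Those counts are observable in re-scoped patients.

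**The tested items are listed by segment.** SAP 15.2.3.1 does not separately list the overall Week 16 percentage, so a test of it is implied rather than stated. The figures above are for overall improvement and do not carry over to segments.

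**The illustration rests on assumed rates and on a placebo arm of 9.** This stands. A reader might infer that the shortfall always takes up most of the effect. It does not: at 40% against 10% conversion it is 35%.

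**Conclusion.** The point holds for the Week 16 comparison of overall endoscopic improvement. The re-scope rule, the denominator and the lack of any Week 16 rule for Week 8 improvers are all in the current text, and nothing elsewhere corrects them. The percentage describes late conversion among each arm's Week 8 non-improvers. Week 16 remission and mucosal healing are affected too, through the removal of Week 8 scores of 0 and 1 and, for healing, an undefined denominator.

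The selection follows from the rule itself, but its size does not. In the five cases at 90% retention, whole-arm differences of 27 to 46 points correspond to reported differences of −5 to 30 points. These figures rest on Phase IIa Week 8 rates from a small study and on assumed conversion and retention. The risk is a misleading secondary result in a dose-finding trial. The primary dose decision is not affected.

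**What to change.** 1. **Comparison with placebo.** In SAP 15.2.1.4, 15.2.1.5 and 15.2.3.1, compare arms on the endpoint being reached at Week 8 or at Week 16. Use all FAS patients in the arm as denominator and count patients with no qualifying endoscopy as failures. The composite follows SAP 15.2.1.1; the denominator is widened to the whole FAS. Record the change in SAP 3.3, since the protocol endpoint is stated at Week 16.
2. **Re-scoped percentages.** Label them as late improvement among Week 8 non-improvers, present them descriptively only, and take them out of the between-arm tests. State the mucosal healing denominator.
3. **Counts of Week 8 but not Week 16.** Drop them for overall improvement or remission and for mucosal healing. Keep the by-segment counts, labelled as re-scoped patients only.

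**Cost.** The change is to the SAP text, with a documented departure from the protocol endpoint. It needs no further endoscopy or data.

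**Downside.** Loss of improvement after Week 8 is not seen. Late remission or healing in patients scored 1 at Week 8 is not observed either, so for those two endpoints the rates are lower bounds. The between-arm difference may also be affected if such patients are unevenly spread across arms.

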15.2.1.6. Reduction Relative to Baseline in Stool Frequency and Rectal Bleeding

Number and percentage of patients in each Mayo stool frequency category will be summarized at every study visit and the number of patients with reduction in stool frequency sub-score relative to baseline will be recorded. The stool frequency sub-score corresponds to the **average** of the 3 most recent daily stool frequencies prior to the visit, rounded to the nearest whole number. The normal stool frequency is subtracted from this average to obtain the Mayo stool frequency sub-score for a particular visit. Frequency of stools will be obtained from e-Diaries completed daily by the patient.

Descriptive statistics for stool frequency sub-score and its change from baseline will be presented by visit.

Document: \\iedc-vnasc01\BIOSdata\Abivax\ABX464\FZA92720\Biostatistics\Documentation\SAP\ABX464-103_SAP_V2.0_10MAY2021

Author: [REDACTED] Version Number: 2.0
Version Date: 10May2021

Template No.: CS_TP_BS016 Revision 5

Reference: CS_WI_BS005

Effective Date: 01Apr2018

The frequency sub-score will be calculated as described above. Reduction relative to baseline is defined in Section 6.6.

Number and percentage of patients in each rectal bleeding category will be summarized. The number of patients indicating an improvement in rectal bleeding sub-score from the baseline rectal bleeding sub-score will be recorded. The rectal bleeding sub-score corresponds to the **worst category** of the 3 most recent values prior to the visit.

Only days when both the number of stool and the rectal bleeding are available will be considered for the calculation. If some data are missing from the most recent consecutive 3 days preceding the visit, then data from the next closest days within 7 days before the visit will be used for calculation.

15.2.1.7. Reduction Relative to Baseline in pMMS at every Visit and MMS at Week 16

Partial MMS will be assessed at every visit, and MMS at Screening, Week 8 and Week 16. Partial MMS is the sum of the stool frequency and rectal bleeding sub-scores of the MMS.

The screening MMS will be used as baseline MMS. Day 1 pMMS will be used as baseline pMMS. Absolute scores and change from baseline will be summarized by treatment arm, and the number of patients with a reduction relative to baseline in the scores will be recorded. Reduction relative to baseline is defined in Section 6.6

15.2.1.8. Global Effect of ABX464 Treatment vs Placebo in Change from Baseline in MMS at Week 8 and Week 16 and in pMMS at every study visit

The global effect of ABX464 treatment will be assessed by comparing the MMS scores at Week 8 and Week 16 and pMMS scores at every visit of the active treatment groups combined vs placebo group.

Document: \\ieddc-vnasc01\BIOSdata\Abivax\ABX464\FZA92720\Biostatistics\Documentation\SAP\ABX464-103_SAP_V2.0_10MAY2021

Author: [REDACTED] Version Number: 2.0
Version Date: 10May2021

Template No.: CS_TP_BS016 Revision 5

Reference: CS_WI_BS005

Effective Date: 01Apr2018

15.2.1.9. Reduction relative to Baseline in Fecal Calprotectin and CRP Levels at Week 8 and Week 16

Change from baseline in Fecal Calprotectin and CRP levels will be determined at Week 8 and Week 16. The number of patients with a reduction relative to baseline in Fecal Calprotectin and CRP levels will also be recorded. Reduction relative to baseline is defined in Section 6.6.

15.2.1.10. The Inflammatory Bowel Disease Questionnaire Scores and Change from Baseline at Week 8 and Week 16

The IBDQ is used to asses QoL in patients with inflammatory bowel diseases (IBD). It contains 32 questions covering four health domains (bowel symptoms, systemic symptoms, emotional function and social function) and scores for each question range from 1 (worst case) to 7 (best case). The total IBDQ score ranges from 32 to 224, with higher scores reflecting better well-being. The total scores and change from baseline will be determined at Week 8 and Week 16 and summarized by treatment arm.

15.2.1.11. Reduction relative to baseline of infiltrate/histopathology (rectal biopsies) using the Robarts Histopathology Index (RHI), the Geboes and Nancy Histology Scoring Scales at Week 8 and Week 16

Change from baseline in RHI, Geboes and Nancy scores will be determined at Week 8 and Week 16. The number of patients with a reduction relative to baseline in RHI, Geboes and Nancy scores will also be recorded. Reduction relative to baseline is defined in Section 6.6.

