7.3. MISSING DATA

A subject's missing efficacy data viz. MMS (or any components of MMS missing) at Week 8, will be imputed and the subject will be considered as a non-responder for clinical remission and response.

Missing MMS components at Week 8 will be imputed as follows:

Stool Frequency Sub score: The average of the 3 recent eDiary stool frequency records (if no prior records then choose records after the Week 8 visit date) within 10 days of date of week 8 visit is calculated. The normal stool frequency (at screening) is subtracted from the average and rounded to a whole number. The imputed sub score will be assigned as follows:.

Sub score=0; if calculated value =0

Sub score=1; if calculated value=1,2

Sub score=2; if calculated value=3,4

Sub score=3; if calculated value=5 or greater

If no records available within 10 days from eDairy, the nearest neighbour method will be considered.

Rectal Bleeding Sub score: The worst of the 3 recent eDiary records within 10 days of Date of Week 8 visit, will be considered as the analysis value (if no prior records then choose records after the Week 8 visit date) . If no records available within 10 days from eDairy, the nearest neighbour method will be

Document: \\iedc-vnasc01\BIOSdata\Abivax\ABX464\FZA92720\Biostatistics\Documentation\SAP\ABX464-103_SAP_V2.0_10MAY2021

Author: [REDACTED]

Version Number:
Version Date:

2.0
10May2021

Template No.: CS_TP_BS016 Revision 5

Reference: CS_WI_BS005

Effective Date: 01Apr2018

considered.

Mucosal appearance at Endoscopy: The analysis value of the nearest neighbour is used to impute missing Endoscopy sub score. The nearest neighbour is defined as the subject in Placebo arm with non-missing sub score, matching the 'subject with missing value' by Gender, Baseline MMS, Age and Previous Exposure to other biologics/JAK status. The matching score is calculated for all the placebo subjects with non-missing sub score, as follows:

- 1) If the subject matches in gender, 5 points assigned.
- 2) If previous exposure status matches, then additional 5 points.
- 3) The absolute difference between the Baseline MMS and Age, is subtracted from the scores.

The Placebo subject with the highest score is considered the nearest neighbour. In case of tied nearest neighbour scores, the worst sub score value will be used to impute.

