15. EFFICACY OUTCOMES

15.1. PRIMARY EFFICACY

15.1.1. PRIMARY EFFICACY VARIABLE & DERIVATION

The primary efficacy variable is the reduction from baseline in MMS at Week 8 (Day 57).

The MMS will be obtained from the MMS eCRF page with raw.MMS.MMSSCR and confirmed by eDiary entries. The MMS ranges from 0 to 9 and is derived from the sum of 3 sub-scores ranging from 0 to 3 for stool frequency, rectal bleeding and mucosal appearance at endoscopy respectively, with a lower score indicating less severe or no ulcerative colitis (UC) (See APPENDIX 2). The MMS determined at screening will be used as baseline MMS, as MMS is not calculated at Day 1.

Change from baseline is described in Section 6.6.

Document: \\ieedc-vnasc01\BIOSdata\Abivax\ABX464\FZA92720\Biostatistics\Documentation\SAP\ABX464-103_SAP_V2.0_10MAY2021

Author: [REDACTED]

Version Number: 2.0
Version Date: 10May2021

Template No.: CS_TP_BS016 Revision 5

Reference: CS_WI_BS005

Effective Date: 01Apr2018

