APPENDIX 2. MAYO SCORE

Components of the Mayo Score	
Stool frequency	
0	Normal
1	1–2 stools/day more than normal
2	3–4 stools/day more than normal
3	5 or more stools/day more than normal
Rectal bleeding	
0	None
1	Visible blood with stool less than half the time
2	Visible blood with stool half of the time or more
3	Passing blood alone
Mucosal appearance at endoscopy	
0	Normal or inactive disease
1	Mild disease (erythema, decreased vascular pattern, mild friability)
2	Moderate disease (marked erythema, absent vascular pattern, friability, erosions)
3	Severe disease (spontaneous bleeding, ulceration)
Physician rating of disease activity	
0	Normal
1	Mild
2	Moderate
3	Severe

Document: \\ieedc-vnasc01\BIOSdata\Abivax\ABX464\FZA92720\Biostatistics\Documentation\SAP\ABX464-103_SAP_V2.0_10MAY2021

Author: [REDACTED] Version Number: 2.0
Version Date: 10May2021

Template No.: CS_TP_BS016 Revision 5

Reference: CS_WI_BS005

Effective Date: 01Apr2018

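### SAP 15.2.1.6 takes the raw difference from normal stool frequency as the by-visit Mayo stool sub-score, without the 0–3 bands, and SAP 7.3 gives no imputed Week 8 score to a patient below normal

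*SAP*

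**What the plan says.** SAP 15.2.1.6 derives the secondary endpoint on stool frequency and rectal bleeding, with stool counts taken from the e-Diary. It promises category output: "Number and percentage of patients in each Mayo stool frequency category will be summarized at every study visit". For the sub-score itself it takes the average "of the 3 most recent daily stool frequencies prior to the visit, rounded to the nearest whole number", and then says "The normal stool frequency is subtracted from this average to obtain the Mayo stool frequency sub-score for a particular visit". The section later refers back to this calculation for the descriptive statistics and change from baseline. It never converts the difference to a 0–3 score and does not cite Appendix 2.

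SAP Appendix 2 defines the sub-score by bands. Score 0 is normal, score 1 is "1–2 stools/day more than normal", score 2 is "3–4 stools/day more than normal", and score 3 is five or more above normal. Protocol Appendix 3 has the same table.

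For the primary variable, SAP 15.1.1 says "The MMS will be obtained from the MMS eCRF page with raw.MMS.MMSSCR and confirmed by eDiary entries", adds "The MMS ranges from 0 to 9 and is derived from the sum of 3 sub-scores ranging from 0 to 3", and refers to Appendix 2.

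SAP 7.3 does write the bands out as a computing rule, but only for components missing at Week 8. Its zero band reads "Sub score=0; if calculated value =0" and the next band starts at 1. The nearest-neighbour fallback for the stool component applies only when there are no diary records within 10 days of the Week 8 visit.

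**The concern.** A difference in stools per day is not a Mayo sub-score. It has no upper limit and can be negative. If the 15.2.1.6 sentence is programmed as written, four results are affected:

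- the by-visit stool sub-score;
- its change from baseline;
- the number of patients with a reduction, which SAP 6.6 defines as any change below zero and SAP 15.2.3.1 sends on to model-based analysis;
- the partial Modified Mayo Score (pMMS), wherever its stool part is computed or estimated from the diary outside Week 8. SAP 15.2.2 uses diary entries to estimate missing stool scores for secondary variables. The bands in 7.3 stop at Week 8, so 15.2.1.6 is the only written computing rule for the other visits.

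The gap in 7.3 is a separate matter. A patient with a missing Week 8 stool sub-score, usable diary records and a rounded average below his or her own normal matches no band and does not qualify for the fallback. Imputed components feed the Week 8 MMS, so this gap does reach the primary endpoint.

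**Working it through.** Let d be the rounded three-day average minus the patient's normal frequency.

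**Rules compared**

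- SAP 15.2.1.6, read literally: sub-score = d.
- SAP Appendix 2: 0 for normal; 1 for d = 1–2; 2 for d = 3–4; 3 for d ≥ 5.
- SAP 7.3 (missing Week 8 only): 0 for d = 0; 1 for d = 1–2; 2 for d = 3–4; 3 for d ≥ 5.
- Assumption: d < 0 scores 0. Appendix 2 does not name this case.

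**The plan's own figure.** With the Appendix 2 bands, the largest MMS is 3 + 3 + 3 = 9 and the smallest is 0. This reproduces the 0–9 range in SAP 15.1.1.

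**Enumeration**

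| d | 15.2.1.6 literal | Appendix 2 | 7.3 | Literal minus Appendix 2 |
|---|---|---|---|---|
| −1 | −1 | 0 (assumed) | none | −1 |
| 0 | 0 | 0 | 0 | 0 |
| +1 | 1 | 1 | 1 | 0 |
| +2 | 2 | 1 | 1 | +1 |
| +3 | 3 | 2 | 2 | +1 |
| +4 | 4 | 2 | 2 | +2 |
| +5 | 5 | 3 | 3 | +2 |
| +6 | 6 | 3 | 3 | +3 |
| +8 | 8 | 3 | 3 | +5 |

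The literal rule is wrong at 4 of the 6 integer differences from 0 to +5, and at 9 of the 11 from 0 to +10. The 7.3 bands agree with Appendix 2 at every d ≥ 0 and are undefined at every d < 0.

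**Effect on pMMS.** The banded maximum is 3 + 3 = 6. With rectal bleeding 2 and d = +8, the literal rule gives 8 + 2 = 10 and the bands give 3 + 2 = 5.

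**Effect on change and reduction**

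- From +8 to +2: literal 2 − 8 = −6; banded 1 − 3 = −2.
- From +8 to +6: literal 6 − 8 = −2, counted as a reduction under SAP 6.6; banded 3 − 3 = 0, not a reduction.

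**Rounding order.** 15.2.1.6 rounds before subtracting and 7.3 rounds after. For three-day totals of 0 to 45 and whole-number normal frequencies of 1 to 5, the two orders never differed. This is not part of the problem.

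**Reach of the 7.3 gap.** Protocol 9.4 planned for 5% dropout before the Week 8 assessment: 0.05 × 61 ≈ 3 patients per arm, with somewhat more expected because of the pandemic. Only those who also have diary records near the visit and fall below normal would be affected. The documents do not say how many that is.

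**The case against.** The best defence is that banding was plainly intended. 15.2.1.6 speaks of Mayo categories and of the Mayo sub-score, Appendix 2 defines these on 0–3, and 7.3 writes the bands out. A raw difference would soon produce impossible values, so this could be called an omitted cross-reference. The point about intention stands. But the sentence is an explicit rule, it is referred back to, and it conflicts with another part of the same plan. Not every consequence shows itself, either: an inflated count of patients with a reduction looks like any other count.

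Several stronger readings are tempting, and the documents do not support them:

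- *The primary score is wrong for most patients.* The observed MMS is read from the eCRF, its sub-scores are stated as 0–3, and 15.1.1 refers to Appendix 2. The 15.2.1.6 rule could reach it only through the diary confirmation, and the SAP states no recalculation or replacement rule for that step. The counts above are of possible differences, not patients; no distribution of differences is given.
- *Observed and imputed Week 8 MMS are on different scales.* Both are sums of 0–3 sub-scores.
- *The 7.3 gap costs patients remission or response.* A patient with missing Week 8 MMS data is already a non-responder under SAP 7.3, whatever value is imputed.
- *Remission is misjudged at +2, where the literal 2 fails the limit of 0 or 1 and the banded 1 meets it.* The arithmetic is right, but it matters only if remission is programmed from the 15.2.1.6 sentence instead of the eCRF sub-scores, which the SAP does not say.
- *The error rivals the assumed drug effect of 2.5 − 1.0 = 1.5 points.* That compares a possible error in one patient with a difference in means. No between-arm bias has been shown.

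**Conclusion.** The point holds as a wrong computing rule in a secondary-endpoint section, together with a narrow gap in the Week 8 imputation. Followed as written, 15.2.1.6 gives the correct stool sub-score only at differences of 0 and +1 and overstates it by 1 to 5 points at the differences from +2 to +8 shown. The error would carry into change from baseline, reduction counts and any diary-based pMMS outside Week 8. How far published results would move depends on how the programming was done and on the distribution of differences, and neither is in the documents.

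The 7.3 gap affects only the imputed continuous MMS and pMMS at Week 8, probably in few patients. A below-normal value is possible, since Protocol 6.9.1 allows stable antidiarrheals, but nothing shows that it is common. Treating below normal as score 0 is a reasonable inference that Appendix 2 does not state. The change is worth making because the conflict is explicit and the repair is nearly free.

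**What to change.** 1. In SAP 15.2.1.6, replace the subtraction sentence with the Appendix 2 bands applied to the rounded difference: 0 or less scores 0; 1–2 scores 1; 3–4 scores 2; 5 or more scores 3.
2. In SAP 7.3, change the zero band to a calculated value of 0 or less, and state that below normal is taken to count as normal.
3. Before database lock, check the stool sub-scores on the eCRF (raw.MMS.MMSST) against this rule using the diary.

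The cost is one sentence in each of two SAP sections and one programmed check. No new data are needed, and neither the primary model nor the sample size changes.
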